5.6.2 HANDLING OF PARTICIPANT WITHDRAWALS

The reason for participant discontinuation or withdrawal from the study will be recorded on the relevant eCRF.

A participant will be considered lost to follow-up if he or she fails to attend any scheduled study visit and study staff are unable to contact the participant after at least 5 attempts.

The following actions must be taken if a participant fails to attend any required study visit:

- Study staff will attempt to contact the participant, reschedule the missed visit, counsel the participant on the importance of maintaining the assigned visit schedule and ascertain if the participant wishes to and/or should continue in the study.
- Before a participant is deemed lost to follow-up, the investigator or designee will make every effort to regain contact with the participant (where possible, telephone calls or e-mail – if no answer leave a voicemail on the first and last attempt). These contact attempts will be documented.
- Should the participant continue to be unreachable, he or she will be considered to have withdrawn from the study with a primary reason of lost to follow-up.

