3 OBJECTIVES AND ENDPOINTS

Aim 1: To assess the feasibility and acceptability of Outreach-ER.

• Recruitment rate• Participation rate• Completion rate• Session completion rate• Questionnaire specific response rate
Aim 2:
Care Partners

• Rate of completion for all scales• Exploratory- effectiveness
PLWD

• 30-day hospital readmission rate

- Number of ED visits in 6 months before and 3-month period following the intervention
- Number of ED to Hospital admission in 6 months before and 3-month period following the intervention
- Number of Clinic visits (planned/unplanned) 6 months before and in a 3-month period following the intervention

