8.2.2 DEFINITION OF SERIOUS ADVERSE EVENTS (SAE)

Adverse events are classified as either serious or non-serious. A serious adverse event is any event that results in:

- Death.
- Life-threatening situation.
- Hospitalization or prolongation of hospitalization.
- Disability or incapacitation.

Other events determined by investigator to be medically significant in which subject's well-being is jeopardized (e.g. events that have high likelihood of escalating to the point of meeting criteria outlined above.

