8.2.4 TIME PERIOD AND FREQUENCY FOR EVENT ASSESSMENT AND FOLLOW-UP

Upon consenting, a subject is considered to be a participant in the study, and until that person either withdraws or completes study, AEs and SAEs will be recorded. The investigational team will promptly report any AE/SAE as required per federal guidelines.

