Aim 2: The completeness of the CES-D-10, ZBI-12, and PSS outcomes will be quantified by calculating the rate of CPs that respond to all items on each scale (CES-D-10: 10 items, ZBI: 12 items, PSS: 10 items) at each assessment. The rate of completion for both scales will be presented overall and stratified by questionnaire and by CP demographics. Preliminary efficacy analysis will utilize the total scores for the CES-D-10 (range: 0 to 30), ZBI (range: 0 to 48), and PSS (range: 0 to 40) calculated for all completed questionnaires. All outcomes will be summarized at both questionnaire timepoints using means and/or

medians, as appropriate. Change over the study timeframe (Q2-Q1) will be calculated for each CP and summarized for the sample. To evaluate change in efficacy outcomes, the pre and post scores of each instrument will be compared using paired t-tests. If there is no difference in outcomes, we expect Scorepre = Scorepost.

To determine the feasibility of collecting utilization outcomes, the proportion of enrolled CP/PLWDs who are eligible and consent to research access will be calculated. We will collect utilization data from the EHR including number of inpatient, outpatient, and ER visits for the PLWD in the 6 months before and the 3 months during as well as after participation. These counts will be summarized to describe the patterns in utilization associated with participating in the Outreach-ER programming.

Sensitivity analysis will remove those who do not complete the intervention (early withdrawal or <6 sessions). All analysis will be performed in SAS 9.4 and significance determined using a two-sided alpha of 0.05.

To explore the feasibility of obtaining online consent for research access to CP healthcare utilization records. healthcare utilization as an outcome in a full-scale ePCT. Any differences in CP/PLWD demographics between enrollees who opt-in and those who do not will be assessed.

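### The lost-to-follow-up code is assigned, and SAE recording ended, without a check of the health record, so a death or admission can be filed as loss of contact

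*Combined protocol and SAP*

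**What the plan says.** The trigger for loss to follow-up in Section 5.6.2 is a participant who "fails to attend any scheduled study visit and study staff are unable to contact the participant after at least 5 attempts". Before that, "the investigator or designee will make every effort to regain contact with the participant", with telephone and e-mail named as the means and each attempt documented. If this fails, "he or she will be considered to have withdrawn from the study with a primary reason of lost to follow-up". No minimum period for the attempts is given, and no chart review, proxy contact or vital-status check is named.

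Section 8.2.4 sets the safety window. It opens at consent, and "until that person either withdraws or completes study, AEs and SAEs will be recorded". The serious events in Section 8.2.2 include death and "Hospitalization or prolongation of hospitalization".

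Section 9.1 (Aim 2) plans an EHR extraction: "We will collect utilization data from the EHR including number of inpatient, outpatient, and ER visits for the PLWD", covering a period "in the 6 months before and the 3 months during as well as after participation". Section 3 lists the "30-day hospital readmission rate" among the PLWD endpoints. Section 5.6.1 keeps withdrawal for a medical condition or event separate from withdrawal for loss of contact.

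**The concern.** Every PLWD enters this pilot after a recent emergency visit or admission, and readmission is one of its endpoints. A new admission, or a death, is thus a foreseeable reason why a visit is missed and calls go unanswered. Section 5.6.2 nevertheless assigns the loss-of-contact reason without asking whether one of these has happened, and that code then closes the safety record under Section 8.2.4.

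Two outputs are at stake. The SAE log may omit events in the participants whose status is least known. The account of why participants did not complete may describe clinical deterioration as loss of engagement, and a larger trial would be planned on that account. No other stated step clearly catches the omission: there is no data safety monitoring board (Section 10.1.4), and the back-up for early withdrawals in Section 9.1 is a telephone call to collect acceptability data, which does not reach someone who is not answering.

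**Working it through.** The point is procedural and the plan states no figure to reproduce, so the check is to read the sections together.

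**Step 1: what the lost-to-follow-up code does.** Section 5.6.2 equates loss to follow-up with withdrawal. Section 8.2.4 stops recording at withdrawal. Together, the code ends the SAE window. For a participant who completes, Section 4.3 places completion 3 months after the final study visit, so SAE recording runs to that date. For a lost participant it ends when the code is assigned.

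**Step 2: where an event in the PLWD would be seen.**

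| Event | Inside the 8.2.4 window? | Detected by a step in 5.6.2? | In the 9.1 EHR counts? |
|---|---|---|---|
| Admission before the code | Yes | No step requires it | May be counted |
| Death before the code | Yes | No step requires it | Not a listed item |
| Admission after the code | No | No step requires it | May be counted, if extraction continues |
| Death after the code | No | No step requires it | Not a listed item |

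Events before the code belong in the SAE log but may never be found. Events after it are excluded by rule.

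**Step 3: whether the EHR extraction closes the gap.** Section 9.1 does not say whether extraction continues for participants coded as lost, whether it is done before the code, whether it can correct the withdrawal reason, or whether admissions found there are entered as SAEs. An admission could therefore be counted as utilization, be absent from the SAE log, and belong to a participant recorded as simply out of contact.

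**Step 4: effect on the progression measure.** The completion rate in Section 9.1 is c/b: those completing the intervention over those starting it. The withdrawal reason enters neither count, so c/b is the same under either code. Only the explanation for b − c changes.

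**Step 5: size.** The documents give neither the number who will be lost to follow-up nor the risk of death or admission among them. As an illustration, assume k lost participants, each with a PLWD at independent risk p of such an event. The chance of at least one event is 1 − (1 − p)^k.

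- k = 1: 5% at p = 5%; 30% at p = 30%.
- k = 3: 1 − 0.95³ = 14.3%; 1 − 0.70³ = 65.7%.
- k = 6: 1 − 0.95⁶ = 26.5%; 1 − 0.70⁶ = 88.2%.

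The largest k is 20% × 30 = 6, from the reduced-sample scenario in Section 9.2. That scenario covers drop-out for any reason and is not a forecast of lost contact. All values of p are assumptions. A range of 5% to 88% shows only that the size cannot be fixed from the documents.

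**The case against.** The strongest reply is that the plan does look at the chart. Section 9.1 schedules EHR collection of inpatient, outpatient and ER visits, and readmission is an endpoint. A reader might infer from Section 5.6.2 that no chart check exists anywhere. That is not supported: the absence is confined to the lost-to-follow-up steps, and an admission in that EHR may well reach the utilization table. What remains is that the extraction omits death and is linked to neither the withdrawal reason nor the SAE log.

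A reader might also infer that an admission just before a missed visit is shut out of the safety record. It is not. It occurs before withdrawal, so it lies inside the Section 8.2.4 window; the difficulty is that nothing requires staff to find it. Only later events are excluded.

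The rule is also softer than it may appear. Five attempts is a minimum, every effort at contact is required, and a primary reason does not bar a secondary one. It is written for a participant, not a dyad; how one member's loss affects the other is not stated. These points stand, but none adds a step that would reveal a death or admission.

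Finally, this is a small, single-arm, minimal-risk pilot. That limits the consequence, and it also makes the remedy small.

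**Conclusion.** The point holds as a gap between three sections. Section 5.6.2 assigns the code on failed contact alone, Section 8.2.4 ends SAE recording at that code, and the Section 9.1 extraction is connected to neither. Following the rules as written, a death or admission can be recorded as loss of contact and left out of the SAE log. The case is stronger for death than for admission, because death is not among the listed EHR items.

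The effect is on the SAE record and the reasons for non-completion. A reader might go further and conclude that the progression result is biased, that unanswered calls usually signal a clinical event, or that a definite share of dyads would be misclassified. The documents support none of these: c/b does not depend on the reason code, no section describes why participants become unreachable, and no event rate is given. The size is unknown.

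The conclusion assumes that no study document outside those reviewed, such as a consent form or operating procedure, already requires the check.

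**What to change.** 1. In Section 5.6.2, require that before the lost-to-follow-up code is assigned, and where EHR access is consented, staff check the PLWD's record for death, admission or an emergency visit. If one is found, record it as the reason and enter it in the AE/SAE log.
2. In Section 8.2.4, state that for participants lost to follow-up who have not revoked permission, SAEs ascertained from the EHR are recorded to the planned end of participation. State also how that date is set when there is no final visit.

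The first change concerns the recorded reason and the event log. Whether a participant then remains in the study is a separate decision and need not be settled here.

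The cost is two protocol sentences and a few chart look-ups in at most 30 dyads. Section 9.1 treats consent to research access as something to be measured, so access may not cover everyone, and the consent form should be checked for permission to look after contact is lost. Events outside the health system, events in dyads without consented access, and events in the care partner would still be missed.

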6 STUDY INTERVENTION

6.1 STUDY INTERVENTION(S) ADMINISTRATION

All dyads will receive the study intervention – Outreach-ER. Outreach-ER is a psychosocial intervention designed by dementia experts in the field of care partner interventions. The intervention is similar to other care intervention/support programs such as REACH or NYCUI. The Intervention is designed to be delivered over phone/virtual and in-home and will be conducted by Amplio, LLC consultants. The care plan will be personalized to the needs of the care partner/PLWD.

6.2 DISCONTINUATION OF STUDY INTERVENTION

If a significant change is noted, or any other reason as identified after enrollment, the investigator or qualified designee will determine if any change is needed for the intervention.

7 STUDY SCHEDULE

7.1 SCREENING

7.1.1 SCREENING/CONSENT VISIT (VISIT 1) (DAY 0)

- This visit may be a telephone/video visit
- Review, obtain and document consent from care partner and PLWD (e-consent)
- Review medical history, demorgraphics to determine eligibility to participate
- Schedule the next two study visits for individuals who are eligible and available for the duration of the study
- A total time of 40 minutes to an hour is anticipated for this visit

7.2 BASELINE (VISIT 2) (WITHIN 10 DAYS OF VISIT 1)

- This is a virtual visit
- A REDcap survey is sent via email including the outcome measures CES-D-10, PSS, ZBI-12
- In the case of participants unable to do via email, research staff will conduct this survey via a telephon/video visit
- This visit is about 15-30 minutes.

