5.5 STRATEGIES FOR RECRUITMENT AND RETENTION

Recruitment: A recruitment letter and flyer will be sent out to patients identified as eligible. Within a few days after discharge (2 days to 2 weeks) research staff will reach out to patients and their caregivers via a phone call. If interested, the caregiver and patient will be provided with informed consent to review on their own time. A video or phone encounter will be arranged to provide additional details of the study and informed consent. Participating subjects will need to explain in their own words what the study entails. A virtual consent through REDcap or a mailed consent with witness will be obtained.

Remuneration: Participants will be provided gift cards totaling \$100 per dyad for completing certain visits of the research study.

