7.3 INTERVENTION VISITS

7.3.1 VISIT 3 (WITHIN 3 MONTHS OF DISCHARGE FROM HOSPITAL)

- This visit may be a telephone/video visit
- Initial visit by Amplio consultants
- Setup intervention visits schedules
- This visit is about 15 minutes.

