7.3.2 VISIT 4 (10 DAYS \pm 5 DAYS AFTER VISIT 3)

- This visit may be a telephone/video visit
- Visit by Amplio consultants
- Initial assessment (Assessment#1) with care partner only
- This visit is about 60-90 minutes.
- Field notes will be collected

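### The pre scores are timed from consent and the program from discharge, with no cap on the interval between them, so untreated change can enter Q2-Q1 and be read as benefit.

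*Combined protocol and SAP*

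**What the plan says.** Three time anchors matter, all in the protocol body.

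- **Outreach.** Section 5.5: "Within a few days after discharge (2 days to 2 weeks) research staff will reach out to patients and their caregivers via a phone call". Families then review the consent form in their own time and a separate encounter is arranged. No latest day for consent is given.
- **Consent and first survey.** Section 7.1.1 sets day 0 at consent: "SCREENING/CONSENT VISIT (VISIT 1) (DAY 0". Section 7.2 dates the first survey from there: "BASELINE (VISIT 2) (WITHIN 10 DAYS OF VISIT 1". Its content is "A REDcap survey is sent via email including the outcome measures CES-D-10, PSS, ZBI-12".
- **Program start.** Section 7.3.1: "VISIT 3 (WITHIN 3 MONTHS OF DISCHARGE FROM HOSPITAL". This is a 15-minute contact whose task is "Setup intervention visits schedules". The first substantive session is Visit 4, 5 to 15 days later: "Initial assessment (Assessment#1) with care partner only".

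Visits 2 and 3 are both booked at Visit 1 (section 7.1.1), but no maximum interval between them is set. The scales are next given at Visit 11, 15 to 30 days after the last intervention visit (section 7.4).

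Section 9.1 defines change as Q2-Q1 and tests each scale with a paired t-test against no change. There is no comparison group (section 6.1) and no adjustment for time since discharge or for the wait.

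**The concern.** Q1 can sit close to the emergency visit or admission while the program starts weeks later. CES-D-10 asks about the past week and PSS about the past month (sections 8.1.2 and 8.1.4). A score taken soon after discharge can therefore describe the acute episode, and its recall period can end well before any program contact.

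If scores fall while the dyad waits, the paired comparison credits that fall to Outreach-ER. If they rise, it hides part of any real benefit. Either way the estimate mixes an untreated interval with the treated one, in a proportion that varies between dyads and that the plan does not record.

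What is at stake is the exploratory effect estimate that the pilot passes to the larger study. The main progression criterion, the completion rate c/b in section 9.1, is unaffected.

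**Working it through.** **1. The plan's own figure.** Section 9.2 gives detectable CES-D-10 changes of 2.1 (N = 30) and 2.4 (N = 24) at SD 4, 80% power and two-sided alpha 0.05. A paired t-test with the noncentral t distribution gives 2.12 and 2.39. The other four cells also reproduce: 1.06 and 1.19 at SD 2, 3.18 and 3.58 at SD 6. So SD 4 is the SD of the change, and the same test can be used in step 5.

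**2. Longest wait the windows allow.** Inputs: outreach on day 2 to 14 after discharge (5.5), Q1 0 to 10 days after consent (7.2), Visit 3 by 3 months (7.3.1). Assumptions: 3 months = 91 days, and consent on the outreach day.

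Gap = 91 − (consent day) − (days from consent to Q1)

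| Consent day | Q1 delay | Q1 day | Gap to Visit 3 |
|---|---|---|---|
| 2 | 0 | 2 | 89 days |
| 2 | 10 | 12 | 79 days |
| 14 | 0 | 14 | 77 days |
| 14 | 10 | 24 | 67 days |

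Counting 3 months as 90 or 92 days moves each entry by one day. Later consent shortens the gap.

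**3. What the participation period leaves.** Visit 3 to Visit 9 is six intervals of 10 ± 5 days: 60 days nominal, 30 minimum. Adding 15 days to Visit 11 gives 75 and 45. The synopsis gives 5-6 months of participation (upper end about 183 days). Section 4.3 places completion 3 months after the final visit.

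- Follow-up included: 183 − 91 − 75 = 17 days from Visit 1 to Visit 3 at nominal spacing; 183 − 91 − 45 = 47 days at minimum spacing.
- Follow-up excluded: with nominal spacing, no optional visit and Visit 11 at 15 to 30 days, 183 − 75 = 108 and 183 − 90 = 93 days. The longest waits in step 2 then fit.

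The documents do not say outright which reading applies.

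**4. Share of the Q1-Q2 interval before the program.** Share = gap / (gap + Visit 3 to Visit 11). At nominal 10-day spacing, Visit 3 to Visit 11 takes 75 to 100 days (60 + 15, up to 70 + 30 with the optional visit).

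- Longest waits: 67/(67 + 100) = 40% to 89/(89 + 75) = 54%.
- Follow-up included, nominal spacing: Visit 2 to Visit 3 is 17 − 10 = 7 to 17 days, so 7/(7 + 75) = 9% to 17/(17 + 75) = 18%.

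**5. What drift would do to the test.** The documents give no recovery course, so the shifts are assumed. With no program effect, the paired t statistic has noncentrality δ√N/SD.

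| Assumed fall δ | δ√30/4 | Significant, N = 30 | Significant, N = 24 |
|---|---|---|---|
| 0.5 | 0.68 | 10% | 9% |
| 1.0 | 1.37 | 26% | 22% |
| 1.5 | 2.05 | 51% | 42% |

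The nominal rate is 5%. All three shifts are below the plan's own detectable change of 2.1.

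**The case against.** **The longest wait may not be reachable.** The synopsis duration read with section 4.3, and with the section 9.1 description of utilization over 3 months during and after participation, suggests that the 5-6 months includes follow-up. Then only about 17 to 47 days separate Visit 1 from Visit 3. This stands as a limit on size. It does not remove the point: the duration line is descriptive, no visit window enforces it, and the shorter figures still leave an untreated interval.

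**Consent on the outreach day is unlikely.** Section 5.5 allows time for review and possibly a mailed, witnessed form, and Visits 2 and 3 are booked together. This also stands. A reader might infer that dyads typically wait 10 to 13 weeks. The documents do not support that: 67 to 89 days is what the windows permit under a favorable consent date, not an expected value.

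**The error rates are not findings about this trial.** A reader might infer a known inflation, and that moving Q1 would bring it back to 5%. Neither follows. Size and direction of drift are assumed, and section 2.1 says that needs in dementia keep changing, so scores could rise. Recovery and regression to the mean between Visit 3 and Visit 11 stay in Q2-Q1 whatever is done with Q1.

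**Little depends on the result.** Effectiveness is exploratory (section 3) and the pilot is not formally powered for it (section 9.2). That is a reason to treat this as a cheap improvement rather than a condition for the study to proceed.

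**Moving Q1 can harm a feasibility endpoint.** Dyads who leave before Visit 3 would have no Q1, which lowers e1/a. This holds against moving the survey, and is why the preferred fix keeps Visit 2.

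**Conclusion.** The point holds as a gap in the assessment schedule. Q1 runs from consent, Visit 3 runs from discharge, and no rule ties them together, so an untreated interval of unset length enters an uncontrolled change score.

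Its size is uncertain. The ceiling of 67 to 89 days rests on same-day consent and a 91-day limit. The figures of about 17 and 47 days between Visit 1 and Visit 3 rest on a 6-month participation period that includes follow-up, at nominal and minimum spacing respectively. The effect on the test depends wholly on assumed drift. The conclusion needs only that some drift before the program is possible and that the plan neither limits nor records the time in which it can occur.

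**What to change.** **Preferred.** Keep the Visit 2 survey where it is and count it for e1/a. Add to section 7.2 that the online survey is re-sent before Visit 3 when Visit 3 falls more than 14 days after Visit 2. In section 9.1, define the pre score in Q2-Q1 as the last score before Visit 3. Report the Visit 2 to Visit 3 interval for each dyad and describe change against it.

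Cost: an amendment to one assessment window and one definition, plus one extra 15-30 minute survey for dyads who wait. Section 9.1 counts two questionnaires, so it should also say that the repeat is not a third one for the response rates. If waits prove short, the repeat is rarely triggered.

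**Alternative.** Set the Q1 window to after consent and within 10 days before Visit 3. This adds no survey, but dyads who leave before Visit 3 would have no Q1 and would count as non-responders in e1/a.

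Neither option touches the timing of Visit 3. Both remove only drift before the program, so the report should still say that change during the program cannot be separated from recovery or regression to the mean.
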